PROTOCOL AMENDMENT SUMMARY OF CHANGES

Amendment: 03

Overall Rationale for the Amendment:

The overall rationale for this amendment is to add a database lock for the final efficacy analysis to account for cases that accrued after the data used for the primary efficacy analysis but before the final immunogenicity and safety assessments. The final database lock for the base study will occur after all immunogenicity and safety data are available.

Summary of Changes Table

Section Number and Name	Name Description of Change	
Primary Reason for Amendment		
4.1 Overall Design	Added the description of an additional database lock after the final efficacy sample assessment in the base study.	To conduct the final efficacy analysis earlier than the final database lock of the base study.

Section Number and Name	Description of Change	Brief Rationale
Additional Changes		
8.5.4 Regulatory Reporting Requirements for SAE	Added note for EU reporting requirements.	To comply with EU CTR regulations.
9.1 Statistical Analysis Plan Summary	Added the description of an additional database lock after the final efficacy sample assessment in the base study.	To conduct the final efficacy analysis earlier than the final database lock of the base study.
9.2 Responsibility for Analyses/In-house Blinding	Added the description of an additional database lock after the final efficacy sample assessment in the base study.	Refer to Section 9.1 rationale.
9.6 Statistical Methods	Added the description of an additional database lock after the final efficacy sample assessment in the base study.	Refer to Section 9.1 rationale.
10.1.3 Data Protection	Added note on global privacy compliance.	To clarify adherence to global privacy compliance.
10.1.8 Data Quality Assurance	Added note for document retention period in the EU	Refer to Section 8.5.4 rationale.
Throughout Protocol	Minor administrative, formatting, editorial, grammatical, and/or typographical changes were made throughout the document.	To ensure clarity and accurate interpretation of the intent of the protocol.

TABLE OF CONTENTS

DO	CUM	IENT H	HISTORY	3
PR	ото	COL A	MENDMENT SUMMARY OF CHANGES	4
1	PRO	OTOCO	OL SUMMARY	13
	1.1	Syno	psis	13
	1.2	Sche	ma	18
	1.3	Sche	dule of Activities	20
	1.	3.1	Scheduled Visits for Base Study	20
	1.	3.2	Scheduled Visits for Study Extension (Placebo Group)	24
	1.	3.3	Scheduled Visits for Study Extension (9vHPV Group)	25
2	INT	RODU	CTION	26
	2.1	Study	y Rationale	26
	2.2	Back	ground	27

1 PROTOCOL SUMMARY

1.1 Synopsis

Protocol Title: A Phase 3, randomized, placebo-controlled clinical study to evaluate the efficacy, immunogenicity and safety of the 9vHPV vaccine in Japanese males, 16 to 26 years of age.

Short Title: Phase 3 study for efficacy against anogenital persistent infection, immunogenicity, and safety of the 9vHPV vaccine in Japanese males

Acronym: Not applicable

08PSXL

Hypotheses, Objectives, and Endpoints:

Hypotheses are aligned with objectives in the Objectives and Endpoints table.

The following objectives and endpoints will be evaluated in Japanese males, 16 to 26 years of age.

Primary Objective	Primary Endpoint
Objective: To demonstrate that a 3-dose regimen of the 9vHPV vaccine will reduce the combined incidence of HPV 6/11/16/18-related anogenital (external genital and intra-anal) persistent infection detected in samples from two or more consecutive visits 6 months (± 1-month window) or longer apart compared with placebo in participants who are seronegative at Day 1 and PCR-negative Day 1 through Month 7 to the relevant HPV type.	HPV 6/11/16/18-related anogenital persistent infection
Hypothesis: Administration of a 3-dose regimen of the 9vHPV vaccine reduces the combined incidence of HPV $6/11/16/18$ -related anogenital persistent infection detected in samples from two or more consecutive visits 6 months (\pm 1-month window) or longer apart compared with placebo (The statistical criterion for success requires that the lower bound of the 2-sided 95% CI of vaccine efficacy is $>0\%$).	
Objective: To evaluate the safety and tolerability of the 9vHPV vaccine.	-Solicited injection-site adverse events (AEs)
	-Systemic AEs
	-Serious adverse events (SAEs)

Secondary Objectives	Secondary Endpoints
Objective: To demonstrate that a 3-dose regimen of the 9vHPV vaccine will reduce the combined incidence of HPV 31/33/45/52/58-related anogenital persistent infection detected in samples from two or more consecutive visits 6 months (± 1-month window) or longer apart compared with placebo in participants who are seronegative at Day 1 and PCR-negative Day 1 through Month 7 to the relevant HPV type.	HPV 31/33/45/52/58-related anogenital persistent infection
Hypothesis: Administration of a 3-dose regimen of the 9vHPV vaccine reduces the combined incidence of HPV 31/33/45/52/58-related anogenital persistent infection detected in samples from two or more consecutive visits 6 months (± 1-month window) or longer apart compared with placebo (The statistical criterion for success requires that the lower bound of the 2-sided 95% CI of vaccine efficacy is >0%).	
Objective : To summarize antibody responses [Geometric Mean Titer (GMT) and percent seroconversion] to each of HPV 6, 11, 16, 18, 31, 33, 45, 52, and 58 at Month 7 in participants who are seronegative at Day 1 and PCR-negative Day 1 through Month 7 to the relevant HPV type, by all participants, heterosexual males (HM) group and males who have sex with males (MSM) group, respectively.	Serum antibody titer to each of HPV 6, 11, 16, 18, 31, 33, 45, 52, and 58

Overall Design:

08PSXL

Study Phase	Phase 3
Primary Purpose	Prevention
Indication	Papilloma viral infection
Population	Japanese males, 16 to 26 years of age
Study Type	Interventional
Intervention Model	Parallel
	This is a multi site study.
Type of Control	Placebo
Study Blinding	Double-blind with in-house blinding
Blinding Roles	Participants or Subjects Investigator
	Sponsor
	Outcomes Assessor

PRODUCT: V503 PROTOCOL/AMENDMENT NO.: 064-03

Estimated Duration of Study	The Sponsor estimates that the study will require approximately up to 7 years from the time the first participant (or their legally acceptable representative) provides documented informed consent until the last participant's last study-related contact.
	The base study of this study is a case-driven study and primary efficacy analysis will be conducted after at least 17 primary efficacy endpoint cases and at least 17 secondary efficacy endpoint cases are collected. After completion of the base study, the participants in the placebo group and participants who did not complete 3-dose regimen of 9vHPV vaccine will be offered an opportunity to start or complete a 3-dose series of 9vHPV vaccine in the extension study.
	For purposes of analysis and reporting, the overall study ends when the Sponsor receives the last laboratory result or at the time of final contact with the last participant, whichever comes last.

Number of Participants:

Approximately 1050 participants will be randomized in 1:1 ratio to receive the 9vHPV vaccine or placebo. The targeted enrollment for MSM is approximately 10% of all participants.

Intervention Groups and Duration:

Arm	Intervention	Unit Dose Strength(s)	Dosage	Route of	Vaccination	Use
Name	Name		Level(s)	Administration	Regimen	
The 9vHPV vaccine	V503 (9vHPV vaccine)	HPV 6/11/16/18/31/33/45/52/58 L1 VLP: 30/40/60/40/20/20/20/20/20	0.5 mL	IM	Day 1, Month 2, Month 6	Test Product
Placebo	Saline for injection	mcg per dose 0.9% sodium chloride	0.5 mL	IM	Day 1, Month 2, Month 6	Placebo
The 9vHPV vaccine (Extension Study)	V503 (9vHPV vaccine)	HPV 6/11/16/18/31/33/45/52/58 L1 VLP: 30/40/60/40/20/20/20/20/20 mcg per dose	0.5 mL	IM	1 dose in Ext: Ext 1 OR 2 doses in Ext: Ext 1 and Month 4 in Ext	Test Product
Placebo (Extension Study)	V503 (9vHPV vaccine)	HPV 6/11/16/18/31/33/45/52/58 L1 VLP: 30/40/60/40/20/20/20/20/20 mcg per dose	0.5 mL	IM	Ext 1, Month 2 in Ext, Month 6 in Ext	Test Product

9vHPV = 9-valent human papillomavirus; IM = Intramuscular; VLP = virus-like particle

Other current or former name(s) or alias(es) for study intervention(s) are as follows: the 9vHPV vaccine, SILGARD®9, GARDASIL®9 and V503.

08PSXL

Total Number of Intervention Groups/Arms	2 intervention groups
Duration of Participation	Each participant will participate in the base study for up to 61 months from the time the participant (or their legally acceptable representative) provides documented informed consent through the final contact. Each participant will receive 3 doses of the 9vHPV vaccine or placebo intramuscularly at Day 1, Month 2, and Month 6. After the completion of vaccination, each participant will be followed every 6 months. This is a case-driven study, and participants will continue in the study until at least 17 primary efficacy endpoint cases and at least 17 secondary efficacy endpoint cases are collected. After at least 17 primary efficacy endpoint cases and at least 17 secondary efficacy endpoint cases have accrued, the initial database lock and unblinding will be performed and notified to the study sites. Following notification, participants remaining in the study (ie, who have not yet completed a Final Visit) will proceed to the Final Visit in the base study promptly (as shown in Section 1.3, and Section 8.12.1.4). Sponsor will notify the participants' vaccination assignment, eligible participants will be offered and consented to enter an extension study, which could last up to 9 months. Participants in the placebo group will receive a 3-dose series of the 9vHPV vaccine. Participants who did not complete a 3-dose series in the base study will be eligible to receive 1 to 2 doses of 9vHPV depending on the doses they had completed. Participants will have a safety phone call 1 month after their last dose in the extension study.

Study Governance Committees:

Executive Oversight Committee	No
Data Monitoring Committee	No
Clinical Adjudication Committee	Yes
Steering Committee	No

Study governance considerations are outlined in Appendix 1.

Study Accepts Healthy Participants: Yes

A list of abbreviations used in this document can be found in Appendix 8.

[figure not shown]
1.2 Schema

The study design is depicted in Figure 1 (Base Study) and Figure 2 (Extension Study).

Figure 1

M6 M7 M12 M18 **M24** M30 M42

Study Design (Base Study)

[figure not shown]
9vHPV = 9-valent human papillomavirus; D = Day; HPV = human papillomavirus; M = Month; PCR = polymerase chain reaction

[figure not shown]
After at least 17 primary efficacy endpoint cases and at least 17 secondary efficacy endpoint cases have accrued, initial database lock and unblinding will be performed and notified to the study sites. Following notification, participants remaining in the study (ie, who have not yet completed a Final Visit) will proceed to the Final Visit in the base study promptly. Under that scenario, participants who have not yet completed a Final Visit will complete the specified procedures in Final Visit in this Schedule of Activities. (See Section 1.3 and Section 8.12.1.4).

¹ After initial database lock and unblinding, examination and sample collection for efficacy assessment should not be

² Even after initial database lock and unblinding, serum sample will be collected. At the Final Visit, serum sample should be collected within the specific day ranges from Day 913 to Day 1277 only from the participant who have not yet completed Month 36.

Figure 2 Study Design (Extension Study)

9vHPV = 9-valent human papillomavirus

¹ Participants who did not complete the 3-dose regimen of 9vHPV vaccine in the base study will be eligible to receive the remaining doses from the series (ie, if they already received 2 doses in the base study, they will receive 1 dose in the extension study and a safety phone call 1 month after the last dose; if they already received 1 dose in base study, they will receive 2 doses which are 4 months apart in the extension study and a safety phone call 1 month after the last dose). For those who do not require a dose at the Extension Visit 2b, the visit will not be conducted.

1.3 Schedule of Activities

1.3.1 Scheduled Visits for Base Study

Visit Number	1	2	3	4	5	6	7	8	9	10	11	12	13	Notes
	Day 1													
Scheduled Day/Month		2	6	7	12	18	24	30	36	42	48	54	60 (Final Visit)	
Visit Window ¹		± 3 Weeks	± 4 Weeks	3 to 7 Weeks Postdose 3				ź	± 1 mo	onth				To calculate visit windows, assume 1 month=30 days and 1 week=7 days
Administrative Procedures														
Obtain Informed Consent	X													
Obtain Informed Consent for Future Biomedical Research	X													Participation in future biomedical research is optional and consent must be obtained before collection of blood (DNA) samples.
Review Inclusion/Exclusion Criteria	X													
Assign Participant Identification Card	X													
Collect Lifetime Medical History (includes substance usage)	X													Substances: Alcohol, tobacco
Update Medical History (new conditions not already recorded as medical history or AEs)		X	X	X	X	X	X	X	X	X	X	X	X	
Collect Lifetime Sexual History	X													
Collect Sexual Activity		X	X	X	X	X	X	X	X	X	X	X	X	Sexual activity will not be collected after initial database lock and unblinding.
Review Prior/Concomitant Medication and Non-study Vaccination Review	X	X	X	X	X	X	X	X	X	X	X	X	X	See Section 6.5 for prerequisites for medications and non-study vaccines

Visit Number	1	2	3	4	5	6	7	8	9	10	11	12	13	Notes
Scheduled Day/Month		2	6	7	12	18	24	30	36	42	48	54	60 (Final Visit)	
Visit Window ¹		± 3 Weeks	± 4 Weeks	3 to 7 Weeks Postdose 3		± 1 month					To calculate visit windows, assume 1 month=30 days and 1 week=7 days			
Clinical and Laboratory Proc	edures													
Measure Oral Temperature	X	X	X											Prior to each vaccination. Participants who have a fever (defined as an oral temperature of ≥37.5°C) within the 24-hour period prior to vaccination must be rescheduled.
Record Height and Weight	X													Prior to vaccination.
Physical Examination (optional, per investigator's discretion; perform if needed to assess inclusion/exclusion criteria)	X													
Anogenital Physical Examination	X													Prior to vaccination
Genitourinary examination for external genital lesions	X			X	X	X	X	X	X	X	X	X	X	Prior to vaccination on Day 1 Examination will not be required after initial database lock and unblinding.
Penile/glans penis file and wetted swab for HPV PCR	X			X	X	X	X	X	X	X	X	X	X	Prior to vaccination on Day 1 Sample should not be collected after initial database lock and unblinding.
Scrotal file and wetted swab for HPV PCR	X		_	X	X	X	X	X	X	X	X	X	X	Prior to vaccination on Day 1 Sample should not be collected after initial database lock and unblinding.
Perianal examination for external genital lesions	X			X	X	X	X	X	X	X	X	X	X	Prior to vaccination on Day 1 Examination will not be required after initial database lock and unblinding.

Visit Number	1	2	3	4	5	6	7	8	9	10	11	12	13	Notes
	Day 1		Month											
Scheduled Day/Month		2	6	7	12	18	24	30	36	42	48	54	60 (Final Visit)	
Visit Window ¹		± 3 Weeks	± 4 Weeks	3 to 7 Weeks Postdose 3		± 1 month							To calculate visit windows, assume 1 month=30 days and 1 week=7 days	
Perineal/perianal file and wetted swab for HPV PCR	X			X	X	X	X	X	X	X	X	X	X	Prior to vaccination on Day 1 Sample should not be collected after initial database lock and unblinding.
Intra-anal wetted swab for HPV PCR	X			X	X	X	X	X	X	X	X	X	X	Prior to vaccination on Day 1 Sample should not be collected after initial database lock and unblinding.
External genital lesion biopsy (if indicated)		X	X	X	X	X	X	X	X	X	X	X	X	Processed and analyzed at Central Laboratory Sample should not be collected after initial database lock and unblinding.
Sexually Transmitted Infection (STI) Testing (local laboratory testing, at the discretion of the investigator if clinically indicated)	X	X	X	X	X	X	X	X	X	X	X	X	X	Optional at any visit
Blood Sample Collection (Serum for anti-HPV)	X			X					X				(X) ²	Prior to vaccination on Day 1 Sample should be collected even after initial database lock and unblinding.
Blood Sample Collection (DNA) for Future Biomedical Research	X													Prior to vaccination from enrolled participants only (optional).
Vaccine Allocation/Randomization	X													
9vHPV Vaccine/Placebo Administration	X	X	X											
30-minute postvaccination observation period	X	X	X											
Provide Vaccination Report Card (VRC)	X	X	X											See Section 8.4.4 for data collected in VRC.

Visit Number	1	2	3	4	5	6	7	8	9	10	11	12	13	Notes
	Day 1					Mon	th							
Scheduled Day/Month		2	6	7	12	18	24	30	36	42	48	54	60 (Final Visit)	
Visit Window ¹		± 3 Weeks	± 4 Weeks	3 to 7 Weeks Postdose 3				=	⊧ 1 mo	onth				To calculate visit windows, assume 1 month=30 days and 1 week=7 days
Review and Collect VRC		X	X	X										Telephone contacts after 15 days from Day 1, Month 2 and Month 6, respectively to remind the participants.
Monitor Adverse Events	X	X	X	X	X	X	X	X	X	X	X	X	X	

Once at least 17 primary efficacy endpoint cases and at least 17 secondary efficacy endpoint cases have been observed, initial database lock and unblinding will be performed and notified to the study sites. Following notification, participants remaining in the study (ie, who have not yet completed a Final Visit) will proceed to a Final Visit in the base study promptly. Under that scenario, participants who have not yet completed a Final Visit will complete the specified procedures in Final Visit in this Schedule of Activities. Details are shown in Section 8.12.1.4.

- At or later than Visit 5, any visit outside of visit window must occur at least 4 months after the previous visit (ie, the minimum length of time between samples to be counted as a case of persistent infection, see Section 9.4.1). Regarding protocol study visit windows, the following situations require consultation between the investigator and the Sponsor and written documentation of the collaborative decision: the study site is considering skipping a visit.
- When the cases would accrue earlier, participants who have not yet completed Month 36 should schedule a Final Visit with collection of serum sample within the specific day ranges from Day 913 to Day 1277, if possible. At the Final Visit, serum sample should not be collected from the participants who have already completed Month 36 or outside of the day ranges from Day 913 to Day 1277.

1.3.2 Scheduled Visits for Study Extension (Placebo Group)

Visit Number	Extension Visit	Extension Visit 2a	Extension Visit 3	Ext Final Status	Notes
Scheduled Day/Month	First Visit of Extension Study	2 (Extension)	6 (Extension)	1 month after last dose in Extension	
Visit Window		± 3 Weeks	± 4 Weeks	± 1 Week	To calculate visit windows, assume 1 month=30 days and 1 week=7 days
Obtain Informed Consent	X				
Review Inclusion/Exclusion Criteria	X				
Measure Oral Temperature	X	X	X		Prior to each vaccination. Participants who have a fever (defined as an oral temperature of ≥37.5°C) within the 24-hour period prior to vaccination must be rescheduled.
9vHPV Vaccine Administration	X	X	X		The first vaccination in the extension study is recommended to occur the same day as the Final Visit of base study, if possible.
30-minute postvaccination observation period	X	X	X		
SAEs and Deaths	X	X	X	X (Phone call)	SAEs and deaths, regardless of causality, will be reported from the time of first vaccination through 1 month after the participant's last vaccination in the extension study.

9vHPV = 9-valent human papillomavirus; SAE=serious adverse event

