The investigator or delegate will train the participant in the use of the VRC at Visit 1 (Day 1). Temperatures, injection-site reactions, other complaints or illnesses, and concomitant medications or vaccinations will be recorded on the VRC by the participant. Participants should be informed to contact the investigator immediately in the event of a hospitalization or visit to another physician.

V503-064-03 FINAL PROTOCOL 24-SEP-2024 Confidential

Participants will use the VRC to document the following information:

- Oral temperatures measured Day 1 (day of vaccination) through Day 5 postvaccination.
 - Participants will record oral temperature in the evening after each study vaccination and daily, at the same time of day, for 4 days after each study vaccination for the purpose of identifying febrile events.
 - Note: If an oral temperature indicates a fever (defined as an oral temperature of ≥ 37.5 °C), the AE of "fever" must be documented in the appropriate eCRF.
- Solicited injection-site AEs (redness/erythema, swelling, and tenderness/pain) Day 1 through Day 5 postvaccination.
- Any other injection-site or systemic AEs Day 1 through Day 15 postvaccination.
- Concomitant medications and non-study vaccinations Day 1 through Day 15 postvaccination.

In order to ensure that the VRC is being filled out without delay, telephone contacts to remind the participant will be conducted after 15 days postvaccination.

All participants will be expected to bring the VRC to the study site at the next scheduled visit. The investigator or delegate will review the data captured on the VRC with the participant at Visit 2 (Month 2), Visit 3 (Month 6), and Visit 4 (Month 7). For the AEs outlined above, the investigator will use the information provided by the participant both on the VRC, and verbally at the time of VRC review, to apply the appropriate assessment of causality as described in Appendix 3. At the time of VRC review at the next scheduled visit, participants will be questioned regarding any new medical conditions that occurred beyond Day 15 postvaccination. The investigator will determine if the medical condition is to be reported as an SAE using the reporting guidelines provided in Section 8.4.

Extension Study:

A VRC will not be utilized for participants enrolled in the extension study and NSAEs will not be collected. SAEs and death will be collected from the first dose of vaccination until 1 month after the last dose.

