Additionally, any SAE brought to the attention of an investigator at any time outside the period specified in the previous paragraph also must be reported immediately to the Sponsor if the event is either:

• A death that occurs before the participant completing the study, but outside the period specified in the previous paragraph.

OR

• An SAE that is considered by an investigator, who is a qualified physician, to be vaccine related.

Investigators are not obligated to actively seek AEs or SAEs or other reportable safety events in former study participants. However, if the investigator learns of any SAE, including a death, at any time after a participant has been discharged from the study, and the investigator considers the event to be reasonably related to the study intervention or study participation, the investigator must promptly notify the Sponsor.

All initial and follow-up AEs, SAEs, and other reportable safety events will be recorded and reported to the Sponsor or designee within the time frames as indicated in Table 3.

Table 3 Reporting Periods and Time Frames for Adverse Events and Other Reportable Safety Events

Type of Event NSAE	Reporting Time Period: Consent to Randomization/ Allocation Report if: - due to protocol- specified intervention - causes exclusion - participant is receiving placebo run-in or other run-	Reporting Time Period: Randomization/ Allocation through Protocol- specified Follow- up Period Report all	Reporting Time Period: After the Protocol- specified Follow- up Period Not required	Time Frame to Report Event and Follow-up Information to Sponsor: Per data entry guidelines
SAE	in treatment Report if: - due to protocol- specified intervention - causes exclusion - participant is receiving placebo run-in or other run- in treatment	Report all	Report if: - drug/vaccine related any death until participant completion of study (Follow ongoing to outcome)	Within 24 hours of learning of event
Cancer	Report if: - due to intervention - causes exclusion	Report all	Not required	Within 5 calendar days of learning of event (unless serious)
Overdose NSAE=nonserious a	Report if: - receiving placebo run-in or other run- in medication dverse event; SAE=serious a	Report all	Not required	Within 5 calendar days of learning of event

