9.6 Statistical Methods

Statistical methods for efficacy and immunogenicity analyses are described in Section 9.6.1 and Section 9.6.2, respectively. The same analysis plan for analysis populations and methods without hypothesis testing will be applied to evaluate decreasing of selected efficacy and immunogenicity endpoints from the first database lock for primary analysis, by using data up to the end-of-base-study (the database lock after the completion of the final efficacy sample assessment for the final efficacy analysis and after the last participant's Final Visit in the base study for the final immunogenicity and safety analysis). Safety analysis approaches are described in Section 9.6.3. Selected safety endpoints will be summarized separately using descriptive methods for Tier 3 events in an end-of-base-study report. Only SAE/death will be summarized separately using descriptive methods in an extension study report. Methods related to exploratory objectives will be further described in the sSAP.

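### In both extension schedules the last safety call may be made up to 7 days before the 1-month SAE/death period that it is meant to cover has ended

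*Combined protocol and SAP*

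**What the plan says.** The SAE/death row of both extension schedules (1.3.2 for the placebo group, 1.3.3 for the 9vHPV group) reads "SAEs and deaths, regardless of causality, will be reported from the time of first vaccination through 1 month after the participant's last vaccination". Sections 8.4.4 and 8.5.1 repeat the period for the extension: "SAEs and death will be collected from the first dose of vaccination until 1 month after the last dose".

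The contact meant to close that period is the Ext Final Status phone call. Both schedules place it at "1 month after last dose in Extension", give it a window of ± 1 week, and add the convention "To calculate visit windows, assume 1 month=30 days and 1 week=7 days". The synopsis describes a single contact after the final dose: "Participants will have a safety phone call 1 month after their last dose in the extension study".

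No diary supplements the call. Section 8.4.4 states "A VRC will not be utilized for participants enrolled in the extension study and NSAEs will not be collected". On analysis, section 9.6 says "Only SAE/death will be summarized separately using descriptive methods in an extension study report". On the time after participation ends, section 8.5.1 says "Investigators are not obligated to actively seek AEs or SAEs or other reportable safety events in former study participants".

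**The concern.** A collection period is actively ascertained only up to the last time somebody asks. Here the period ends 30 days after the last dose, but a site can make its only remaining contact a week earlier and be fully compliant. I found no text that requires an early call to be repeated, or that requires any contact on or after Day 30.

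SAEs and deaths are the only safety outcome that the extension collects. Placebo-group participants receive their planned 9vHPV series there. A 9vHPV-group participant who needs one remaining dose has no contact after the 30-minute observation except this call. What is at stake is whether the extension summary can be read as active SAE follow-up for a full month after the last dose.

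The base study does not have this problem. Its general AE period is Days 1 to 15 after each dose. The reminder call comes after 15 days, and the Month 7 visit opens no earlier than 3 weeks after dose 3. Its SAE period of 6 months after dose 3 falls within a schedule of six-monthly visits.

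**Working it through.** The plan states no figure for this gap, so there is none to reproduce. The check is day arithmetic under the protocol's own convention, with days counted from the dose.

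**Inputs**
- End of SAE/death period: 1 month = 30 days after the last dose (1.3.2, 1.3.3, 8.4.4, 8.5.1).
- Final call: 30 days ± 7 days after the last dose (1.3.2, 1.3.3).
- Placebo-group doses: first extension visit, Month 2 ± 3 weeks, Month 6 ± 4 weeks (1.3.2).
- 9vHPV-group second dose, where needed: Month 4 ± 3 weeks (1.3.3).
- Stated maximum length of the extension: 9 months (1.1).

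**Gap after the last dose**
- Permitted call days: 30 − 7 = 23 to 30 + 7 = 37, which is 15 days.
- Uncovered days = max(0, 30 − call day). A call on Day 23 leaves 7, a call on Day 29 leaves 1, and a call on Days 30 to 37 leaves 0.
- Worst case: 7/30 = 23% of the 30 days after the last dose.
- Even spread over the 15 days (an assumption): early calls 7/15 = 47%. Total uncovered days 7 + 6 + 5 + 4 + 3 + 2 + 1 = 28, so the mean is 28/7 = 4 days per early call and 28/15 = 1.9 days over all calls.

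**Earlier doses**
- Placebo group, dose 1 to the next visit: at least 60 − 21 = 39 days.
- Placebo group, dose 2 to the next visit: at least (180 − 28) − (60 + 21) = 71 days.
- 9vHPV group, first of two doses to the next visit: at least 120 − 21 = 99 days.

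The schedules mark SAEs and deaths at each of these visits. For participants who keep to the schedule, a full month after every dose except the last is therefore asked about.

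**Against the whole extension period**
- Nominal placebo-group period: 180 + 30 = 210 days. Worst case 7/210 = 3.3%; even spread 1.9/210 = 0.9%.

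**Rough size in events (illustration only)**
- Assume that all 525 placebo-group participants enter, and that the 0.5% SAE figure in 9.9.3, which has no stated period, accrues over 45 to 365 days. Then 525 × 0.005 = 2.6 SAEs. The share in uncovered days is 2.6 × 1.9/365 = 0.01 to 2.6 × 1.9/45 = 0.11 SAEs.

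**Room for a later window**
- Latest placebo-group end now: 180 + 28 + 30 + 7 = 245 days (8.2 months).
- With a window of 0 to +1 week: still 245 days. With 0 to +2 weeks: 180 + 28 + 30 + 14 = 252 days (8.4 months). The stated maximum is 9 × 30 = 270 days.

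**The case against.** The strongest objection is that the reporting duty runs with the period and not with the call. Table 3 asks sites to report all SAEs through the protocol-specified follow-up period, so an SAE on Day 27 that reaches the site after a Day 23 call must still be reported. Section 8.5.1 also requires vaccine-related SAEs, and deaths before study completion, to be reported outside the period, and related SAEs to be notified even after discharge. This stands. A reader might infer that the 1-month follow-up is simply not delivered, or that an early call turns the participant into a former participant whose events no longer count. The documents support neither reading. What is lost is active questioning, and only for events that nobody brings to the site.

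A second objection is that the 23% figure flatters the problem. This also stands for the placebo group, where the gap follows the last dose alone and the worst case is 3.3% of the whole period. It has less force for a 9vHPV-group participant who needs one dose, because the 30 days after that dose are the whole follow-up.

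A third objection is that symmetric windows are an ordinary design choice and the output is descriptive. That limits the importance of the point. It does not explain why the sole closing contact may precede the end of the period that it closes.

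A reader might also infer that the extension report will claim a full month of follow-up. No report wording is in the documents, so that is a risk to avoid and not an error already made.

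**Conclusion.** The mismatch is real and small. In both extension groups a compliant call on Days 23 to 29 leaves the last 1 to 7 days of the stated SAE/death period without active ascertainment. The mean of about 1.9 days over all calls, with 47% of calls early, rests on the even-spread assumption; the 7-day maximum rests only on the protocol's windows and calendar convention. The effect is confined to the descriptive extension SAE/death summary. Efficacy hypotheses, type 1 error, power and base-study safety are untouched. It is worth correcting because the correction is cheap and makes the contact cover the period that the protocol states.

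**What to change.** In 1.3.2 and 1.3.3, replace the ± 1 week window for Ext Final Status with a one-sided window that opens 30 days after the last dose. Two options close the gap completely:
- 0 to +1 week: the latest call stays at Day 37, but sites have 8 permitted days instead of 15.
- 0 to +2 weeks: the 15-day width is kept, but the latest call moves from Day 37 to Day 44.

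Both stay within the stated 9 months. The change is one cell in each of two tables, but it is still a protocol amendment and needs ethics review before use (10.1.1).

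If calls have already been made before Day 30, the extension report should give the actual SAE follow-up time after the last dose, by group.
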